Kota Belud is located at west coast of Sabah and was one of the first administrative district in Sabah during British occupation. It is located 70km from Kota Kinabalu, the capital of Sabah. The district has an area of 1,391 square kilometres and a population of 107,243 people (Department of Statistics, Malaysia, 2020). The three main ethnicities in Kota Belud are Bajau, Dusun dan Irranun. There is also a minority of Chinese in this district.

The gender distribution in this district is equal; 50.3% of males and 49.7% of females. Close to two-thirds of the population are between 15-64 years old (64.1%), followed by 30% who are between age 0-14 years old and a small percentage are above 65 years old (5.9%). Most of the population are Muslim, followed by Christianity and Buddhism and others.

The population of interest for this study in Kota Belud is the Bajau community. The Bajaus, are one of the indigenous groups in Sabah that still practises their traditional culture. They are often referred to as “cowboys of the east” as their lifestyle resembles the lifestyle of western cowboys. Their main language for communication is Malay, but the older generation are more familiar in their Bajau dialect. There are 134 villages in Kota Belud and 39 villages of it were dominated by Bajau people (Tahir Z et al., 2003).

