3.8 Selection criteria

The **inclusion criteria** for this study is as follows:

- ✚ A self-reported BQ chewer who has been chewing BQ for the past 6 months with atleast 2-3 chewing episode per week. The ingredient of BQ must include AN without or without smokeless tobacco.
- ✚ Other optional ingredients such as slaked lime and betel leaf are allowed.
- ✚ Age of participant must be 18 year old or above
- ✚ Participants must be residing in study location (Kota Belud, Sabah)
- ✚ Ability to comprehend, converse and read in Bahasa Melayu and their local language (Bajau)
- ✚ Participants who are able to provide written consent and agree to comply with all protocol-specified procedures such as providing saliva samples, participating in five 1-2 hours sessions of intervention over 22 days and agree to attend follow-up sessions on first and third month

The **exclusion criteria** for this study are as below:

- ✚ Non-Malaysian citizen
- ✚ Participants who are not willing to quit the BQ chewing habit at the time of the study
- ✚ Women who are pregnant or nursing at the time of study
- ✚ Individuals with psychiatric illness or special social situations that would limit their compliance with study requirements

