3.10.1.5 Questionnaire, Educational Booklet and Intervention Module Translation

The validated questionnaire, educational booklet and intervention module will later undergo an independent forward-backward translation. Firstly, the validated material (source) will be independently translated using a forward translation technique to the target language '*Bahasa Melayu*' (the national language) by two bilingual linguistic experts. The linguistics will later meet to review their translation together to search for inconsistencies with the original English set. Any difference of opinion will be resolved via reconciliation process, to come out with a single provisional forward translation.

The translated questionnaire, educational booklet and intervention module will then be independently back-translated to English by another two bilingual linguistics. They will compare the back translation and the original form of questionnaire for semantic equivalence. Semantic equivalence is a declaration that two data elements from different vocabularies contain data that has a similar meaning. This will ensure that the provisional forward translation is adequate representation of the original English set.

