The subjects will be assigned into a group of seven participants and the appointments for each group participants will be given across the week. A total of 2 group sessions will be made in a day; a morning session and an afternoon session. Participants will be sought of their preferred time to increase participation in the intervention group.

[figure not shown]

Figure 3.7 Flow of Participants on the Screening of the study (Day 0)

1st Session (Day 1)

On the **1st session of the intervention (Day 1)**, attendance of all eligible and consented participants will be taken at **Checkpoint 1** and the nature of intervention will be introduced through a **brief talk**. The information that the participants will undergo 5 sessions of support and information group designed to assist them to quit BQ chewing habit over 22 days period will be emphasized and they will be reminded that their continuous commitment to the intervention is utmost important to their future cessation.

They will also be briefed that each support session will consume approximately 1-2 hours. It will be conducted by the main researcher in Malay language (Bahasa Melayu) and

translated by trained facilitators into Bajau language verbally. A translation script will be prepared before initiation of the intervention for standardization to minimise bias or any poor explanation in Bajau language.

After the brief introduction, an **educational talk** will be delivered to the study participants by the main researcher. The content of the talk will be based on the topics of the educational booklets (general information regarding AN and BQ, risk associated with BQ chewing behaviour through projection of captivating graphical aids, cessation strategies that are modeled after tobacco cessation and researcher's contact information) but in a more detailed and interactive manner. An aid of Microsoft Powerpoint multimedia presentation will be used. A two-way communication mode will try to be sought throughout the entire talk. Participants will be encouraged to participate actively during the educational talk session. The aim of the educational talk is to increase the chewer's awareness, motivation and to enhance their commitment to cease behaviour. Participants too will be encouraged to share their experience and their feelings of chewing BQ and what are the challenges they face while practicing this habit.

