3.14 Data Collection

3.14.1 Baseline

The facilitators from the Kota Belud Dental Clinic staff will be trained and standardised for the conduct of this study. A training manual will be given to each facilitators. They will be briefed and their understanding on every item of the questionnaire and worksheets will be scrutinised and refined as intended by the study. Any difficult words identified by the facilitators will be changed to a simpler alternative. Translated words into Bajau dialect will be discussed and decided upon for standardisation.

From face-to-face interviews with the participants, information regarding demographics details and baseline information about BQ chewing behaviour, BQ composition, BQ dependency levels, reasons for chewing and readiness and self-perceived barriers to quit will be garnered. Face-to-face interview mode was chosen as a method to complete the questionnaire to obtain a better response rate and to minimise inaccurate response due to illiteracy issues and participant's poor comprehension due to age.

Participant's baseline saliva samples will be gained for biomarker comparison as a method to verify the intervention's self-reported effectiveness. Saliva samples collected will be transported within 2-3 hours to the lab facilities to be stored under -80 °C temperature. The transportation of these saliva samples will be monitored and carried out by the main researcher.

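### Eligibility as worded requires reading Bajau, which no participant procedure uses, and conflicts with the protocol's own provision for illiteracy

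*Protocol*

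**What the plan says.** The inclusion criteria in Section 3.8 of the protocol require "Ability to comprehend, converse and read in Bahasa Melayu and their local language (Bajau". The same list sets "Age of participant must be 18 year old or above" and requires participants to be able to give written consent.

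On written material, Section 3.10.1.5 says that the validated questionnaire, booklet and intervention module will be "independently translated using a forward translation technique to the target language", which is Bahasa Melayu. No Bajau version is planned for participants.

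On spoken Bajau, Section 3.10.3.2 (1st Session) has the main researcher deliver sessions in Malay, "translated by trained facilitators into Bajau language verbally". Section 3.10.2.3 requires facilitators to be conversant in Bajau, chiefly to support older participants. Section 3.2 explains why: "the older generation are more familiar in their Bajau dialect".

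On literacy, Section 3.14.1 gives three reasons for face-to-face interviews: a better response rate, poor comprehension linked to age, and "to minimise inaccurate response due to illiteracy issues".

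**The concern.** An eligibility line should ask only for what the trial's procedures need. This one asks for reading in a language in which participants are given nothing to read. It also asks every participant to be literate, while the data-collection section plans for participants who are not.

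Three things are at stake.

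- **Recruitment.** Some willing chewers would be turned away for no procedural reason.
- **Description.** Objectives i and ii (Section 1.6.2) describe the demographics, dependency, reasons and barriers of users in the community, so who is enrolled shapes the answer. Section 3.6 plans to take every eligible chewer in a village, and a reading filter narrows what that total population means.
- **Generalisability.** The cessation result would carry over less surely to chewers who cannot read.

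The wording is also open to two readings. A screener might apply the word for reading to Malay only, or to both languages, and screeners in different villages could differ.

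**Working it through.** The protocol states no figure on this point, so there is none to reproduce. The check is a comparison of sections, followed by one illustration.

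**1. Which participant tasks need which language skill?**

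| Task | Section | Written Malay | Written Bajau |
|---|---|---|---|
| Baseline and follow-up questionnaires | 3.14.1 to 3.14.3 | No, interviewed face to face | No |
| Educational booklet, both arms | 3.10.1.2, 3.10.1.5 | Yes | No |
| Support sessions | 3.10.3.2 | No, spoken Malay with spoken Bajau | No |
| Worksheets and home trigger logs, intervention arm | 3.10.1.3, 3.10.3.2 | Yes | No |
| Saliva sample | 3.11.1 | No | No |

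The last column is empty throughout. Two Bajau language aids are planned. One is for the sessions: "A translation script will be prepared before initiation of the intervention for standardization". The other is for the interviewers: "Translated words into Bajau dialect will be discussed and decided upon for standardisation". Both standardise what staff say, and participants read neither.

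**2. Is the criterion consistent with the rest of the protocol?** If every enrolled person reads two languages, the illiteracy reason in Section 3.14.1 has nobody to apply to. The education item in Section 3.15.1 and Appendix C offers no formal education as a category, so such participants are foreseen. Sections 3.8 and 3.14.1 cannot both be applied as written.

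**3. Who would be affected?** The protocol gives no literacy rate for Bajau chewers, overall or by age. The nearest figures come from cited surveys: 86.7% of Malaysian chewers above 40 (Section 2.5), and 61.2% of a sample with six years of schooling or less (Section 2.1). Neither measures reading ability, and neither is specific to Kota Belud. Section 2.5 also reports an adjusted odds ratio of 27.2 for dependency at six years of schooling or less. If reading tracks schooling, a reading filter could shift the dependency description downward. The documents support that direction as plausible, but not a size.

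**4. Illustration.** Inputs: total to enrol, 92 (Section 3.4); share f of otherwise eligible chewers who fail the reading line, assumed from 0.10 to 0.50.

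Otherwise eligible chewers needed = 92 / (1 − f), rounded up:

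| f (assumed) | Calculation | Chewers needed |
|---|---|---|
| 0.10 | 92 / 0.90 = 102.2 | 103 |
| 0.20 | 92 / 0.80 = 115.0 | 115 |
| 0.30 | 92 / 0.70 = 131.4 | 132 |
| 0.40 | 92 / 0.60 = 153.3 | 154 |
| 0.50 | 92 / 0.50 = 184.0 | 184 |

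With the four villages tentatively named in Section 3.3, the enrolment target averages 92 / 4 = 23 per village.

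**The case against.** The case for leaving the line largely alone has four parts.

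**Reading Malay has a real use.** The booklet is the control arm's only intervention, supported by one explanation at baseline. The trigger log has to be written at home before each chew, for at least three to four days. Admitting non-readers would leave the control arm with a booklet they can hardly use, while the oral sessions would still work in the other arm. That changes the contrast being tested. This stands, so dropping Malay reading is a trade-off. It does not defend Bajau reading.

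**Recruitment may not be at risk.** Section 3.5 draws matched pairs of villages until the sample size is met, and the four villages are only tentative. A lower yield could be met by adding pairs. This stands: the illustration shows extra effort, not a failed sample.

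**The bilingual provisions also serve readers.** Someone may read Malay and still follow spoken Bajau more easily, and only one of the three reasons for interviews concerns illiteracy. This stands too. The provisions do not exist for non-readers alone.

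**The harm is easily overstated.** A reader might infer that the line shuts out the older chewers at whom the trial is aimed. The documents do not support that: the trial admits all adults from 18, the line turns on reading and not age, greater familiarity with Bajau is not inability to read Malay, and Section 3.10.2.3 expects older participants to be enrolled.

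**Conclusion.** The point holds as a minor inconsistency in the eligibility wording. The Bajau reading requirement can exclude people and does nothing else, and the line conflicts with the illiteracy provision in Section 3.14.1. Those conclusions follow from the text and need no assumption.

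The size is unknown. That the excluded would be mainly older or less schooled is a plausible inference from Sections 2.1, 2.5 and 3.2. The range of 103 to 184 chewers rests wholly on the assumed failure share.

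The effect falls on recruitment, the descriptive objectives and generalisability. The same line applies in both arms, so it does not bias the comparison between them. A reader might go further and conclude that the result would not apply to the main users of betel quid. Without a literacy rate that cannot be shown; at most, applicability to non-readers is limited by an unknown amount.

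**What to change.** Amend the line in Section 3.8 before screening starts:

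1. Delete the requirement to read Bajau.
2. Require comprehension and conversation in Bahasa Melayu or Bajau, since spoken translation is already provided.
3. Reconcile the line with Section 3.14.1 by stating one of two positions: Malay reading is still required for the booklet and home worksheets, or assisted completion is allowed on the same terms in both arms.
4. If non-readers are admitted, align the written-consent criterion, and acknowledge that the booklet-only control would be less usable for them.

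Items 1 and 2 change one line and have almost no downside. The choice in item 3 carries the real cost. Keeping Malay reading preserves the comparator but narrows the population. Dropping it widens the population, but it needs help with home logs, which facilitators cannot give at the moment of each chew, and it weakens the control for those participants. Exclusions made under the present wording could not be repaired after enrolment.

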1.6.2 Objectives of the study

- i. To determine the demographics of BQ chewers, BQ chewing behaviours, BQ composition and BQ dependency levels among its users in a high risk community in Malaysia
- ii. To determine the reasons for BQ chewing, the readiness and self perceived barriers to cease BQ habit among users in a high risk community in Malaysia
- iii. To adapt a BQ cessation program for a Malaysian high risk community
- iv. To evaluate the effectiveness of the adapted BQ cessation program through :

- a) self-reported cessation rates
- b) salivary biomarkers measurements

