2.6 Readiness to Quit Habit among BQ Chewers

From an unpublished study participated by Universiti Malaya (Herzog T et al., 2014) among Malaysian BQ chewers regarding their willingness to quit the habit, 29.2% of the participants felt they should quit but claimed were not ready and 29.3% reported a reduced amount of quid (s) that they chewed. Whereas 20.3% participants were not considering to quit at that moment and 20.6% wished they had never started chewing BQ in the first place.

The mean time of **quit attempts** made were 2.0 ± 3.2 times. The most common methods used for quitting among the participants were self motivation (40.1%) and through cold turkey (19.7%). **Health concerns** were specified as the main reason for quitting the chewing habit (77.3%). Only 3.9% chewers who included tobacco in their quid managed to quit, whereas 96.1% of others who included tobacco in their quids were struggling with the habit and were current chewers. **Inclusion of tobacco into quid** made the BQ quitting

experience more challenging and less successful. Likewise, among chewers who rated that **chewing was an important social event** when hanging out with friends, 96.0% of them were current chewers and only 4.0% were ex-chewers.

Among the participants who were **ex-chewers**, 65.3% were very confident that they will remain as non-chewers, while 31.3% were not sure whether they had quitted the habit for good. Close to quarter of them (22.7%) reported that they will definitely take up the chewing habits again someday.

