3.6 Allocation concealment

In this study, allocation concealment will be done at cluster level. A senior dental officer (SDO) in Kota Belud Dental District Office who is not involved in cluster identification and recruitment will keep the allocation sequence in a brown envelope in his or her SDO's office until the matched pair are ready to be recruited into the study.

The allocation sequence will be generated by a statistician employed at the Faculty of Dentistry, Universiti Malaya using computer generated tables. The information will be kept confidential until the intervention are assigned to the villages.

Within the cluster, a universal sampling technique will be used to recruit participants into the study. Universal sampling is also known as a total population sampling; which is a type of purposive sampling that involves examining the entire population that have a particular set of characteristics (Laerd Statistics, 2012). All eligible participants who fulfilled the inclusion and exclusion criteria through the screening session will be recruited as study sample. Thereafter, informed consent will be obtained from the participants.

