3.10.3.2 Implementation of the Study

Control Group

The community screening program for the control group will be organised at the community hall. Villagers who attended the screening program will first be registered and screened for eligibility to participate in the study (**Checkpoint 1**). The eligible participants will be briefed on the nature of the intervention and will be invited to participate. A copy of 'Patient Information Sheet' (PIS) (Appendix A) will be explained and given for reference about the study details and written informed consents (Appendix B) will be obtained from the villagers prior admitting them into the study.

Only consented participants will be interviewed by the trained interviewers (**Checkpoint 2**). Information regarding demographics details and baseline information of BQ chewing behaviours, BQ composition, BQ dependency levels, reasons for chewing, readiness and self-perceived barriers to quit will be obtained. No intra-oral clinical examination will be carried out in this study.

Upon completing of the interview, participants will be given an educational booklet which contains general information regarding AN and BQ, risk associated with BQ chewing behaviour, cessation strategies that are modeled after tobacco cessation and researcher's contact information. After an one-to one explanation about the educational booklet to the participants by the interviewer, they will be ushered to saliva collection counter (**Checkpoint 3**) to provide their baseline saliva sample. Participants will be thanked and given a token of appreciation before they are ushered out of the community hall.

Participants will be provided with an appointment card to return on the 22-day, 1-month and 3-month for follow-up. Follow-up questionnaire and saliva samples will be taken on 22-day and 3-month, whereas a community perception analysis will be performed at 1-

month together with completion of follow-up questionnaire. The summary of participant's flow for the control group is illustrated in Figure 3.6.

[figure not shown]

Figure 3.6 Summary of Participant's Flow for the Control Group in this study

Intervention group

Screening (Day 0)

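### Readiness and barriers are claimed for betel quid users in the community, but only chewers already willing to quit are interviewed

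*Protocol*

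**What the plan says.** Section 1.6.2 of the protocol states two descriptive objectives. Objective i includes "BQ dependency levels among its users in a high risk community in Malaysia", alongside demographics, chewing behaviours and quid composition. Objective ii covers reasons for chewing and "readiness and self perceived barriers to cease BQ habit among users in a high risk community in Malaysia". Research questions A and B in section 1.5 use the same population. Section 4.0 lists the same items as new and updated knowledge on Bajau users in selected high-risk communities.

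Section 3.8 requires a self-reported chewer "who has been chewing BQ for the past 6 months with atleast 2-3 chewing episode per week", who also agrees to saliva sampling, sessions and follow-up. It excludes "Participants who are not willing to quit the BQ chewing habit at the time of the study". Section 3.6 then says: "All eligible participants who fulfilled the inclusion and exclusion criteria through the screening session will be recruited as study sample".

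Section 3.10.3.2 fixes the order in both arms. Villagers are screened for eligibility at Checkpoint 1 and eligible ones are invited to consent. At Checkpoint 2, "Only consented participants will be interviewed by the trained interviewers". That interview uses the baseline questionnaire in Appendix C, whose Section F holds the readiness and barrier items.

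**The concern.** Excluding unwilling chewers suits a cessation trial. The difficulty is that the same selected sample also has to answer descriptive objectives worded for users in the community. For readiness, the selection acts on the very quantity to be described.

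The questionnaire shows the mismatch. Its readiness item still includes an option for people who intend to carry on and accept what follows, and its barrier list includes the view that quitting is not important. The willingness rule removes most of the people who would give those answers.

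If the results are reported under the present wording, a health programme could conclude that Bajau chewers are readier to quit than they are, and that few regard quitting as unimportant. No analysis can recover answers that were never collected, so the matter has to be settled in the protocol before fieldwork.

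**Working it through.** The protocol gives no target or precision figure for objectives i and ii. Its sample size in section 3.4 (38 per arm, 76 in total) belongs to the cessation comparison. It reproduces with the two-sided, continuity-corrected formula for 38.64% against 9.09%, and it does not bear on this point.

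**Step 1. Compare the population claimed with the population observed.**

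| Item | Population claimed (sections 1.5, 1.6.2, 4.0) | Population observed (sections 3.6, 3.8, 3.10.3.2) | How selection acts |
|---|---|---|---|
| Readiness | Users in a high-risk community | Eligible, consented chewers willing to quit | Directly, on nearly the same variable |
| Barriers | Same | Same | Directly on the view that quitting is unimportant; otherwise through correlation with willingness |
| Dependency | Same | Same, and chewing at least 2-3 times a week | Indirectly, and through the frequency threshold |
| Demographics, behaviours, composition | Same | Same | Indirectly, and through the frequency threshold |

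Nothing in the protocol provides for recording these items among chewers screened out as unwilling.

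**Step 2. Direction.** Let u be the share of chewers who are unwilling and screened out. A readiness category with true share p, held only by retained chewers, is observed as p / (1 − u), which exceeds p whenever u > 0. Categories held mainly by unwilling chewers shrink. Readiness is therefore overstated. For dependency and most barriers the documents give neither the size nor the direction of any shift.

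**Step 3. Illustration of size.** Section 2.6 cites an unpublished Malaysian survey in which "20.3% participants were not considering to quit at that moment". The four shares it lists add to 29.2 + 29.3 + 20.3 + 20.6 = 99.4%, which is consistent with non-overlapping categories but does not prove it. Assume the survey applies to these villages and that only the 20.3% count as unwilling:

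- Share retained: 1 − 0.203 = 0.797.
- Inflation of a category held only by retained chewers: 1 / 0.797 = 1.25.
- Example: a true 29.3% would be observed as 29.3 / 0.797 = 36.8%.

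**The case against.** The strongest reply is that objectives i and ii are simply baseline characterisation of a trial sample. Their wording does not say all users or a representative sample. Section 3.1 describes the same measures as participants' baseline information, section 3.6 calls the sampling purposive, and the only hypothesis (section 1.7) concerns cessation. This is a fair account of what the design can deliver. It does not remove the mismatch, because sections 1.5, 1.6.2 and 4.0 still state the wider population. It does point to rewording as the remedy.

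Three stronger readings might be inferred, and the documents do not support them.

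- **That the lowest readiness category must be empty.** The protocol does not define how willingness is judged at screening. A token is given at screening and sessions are paid (section 3.10.3.2), so someone admitted as willing could still choose that option. The other three readiness levels stay open. The barrier option about importance is not the same thing as unwillingness.
- **That objectives i and ii cannot be answered at all.** Most of objective i is not selected on willingness, and the reasons, readiness and barriers of enrolled chewers will be described.
- **That up to half of chewers are removed.** Adding the 29.2% who felt they should quit but were not ready gives 20.3 + 29.2 = 49.5%. The protocol nowhere equates not being ready with not being willing, and the survey's participants included ex-chewers, so its denominator is unclear.

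Even the 20.3% is not an estimate of what happens at Checkpoint 1. Attendance follows a promoted cessation event (section 3.10.3.1), and some unwilling chewers may never come.

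**Conclusion.** The point holds for objective ii and section 4.0, and indirectly for objective i. Readiness among community users will be overstated because chewers unwilling to quit are removed before the only baseline interview, and the least ready answers will be largely depleted. Dependency and the other objective i items are distorted only as far as they correlate with willingness, and through the requirement of chewing at least 2-3 times a week.

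The existence and direction of the bias in readiness follow from the protocol's own order of procedures. Its size is unknown. The figure of about one fifth missing assumes that the survey in section 2.6 applies to these villages and that not considering quitting means the same as not willing to quit. The objective iv comparison of cessation is unaffected, since both arms apply the same criterion. The point should be corrected, but it does not threaten the main result.

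**What to change.** 1. Restate objectives i and ii, research questions A and B and section 4.0 as describing enrolled regular chewers who are willing to quit.
2. At Checkpoint 1, state how willingness is asked, and record and report the number screened out for unwillingness in each village.

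These two changes cost some rewording and one tally on the screening form.

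3. Optionally, put the Section F readiness and barrier items to all consenting chewers at Checkpoint 1, before the willingness criterion is applied. Report that group as screening attendees, not as all community users, because it still reaches only people who come to a promoted cessation event. This takes a few minutes per person from the same staff on the same day. It also needs its own consent wording and an ethics submission: section 3.16 records faculty approval as already given and national approval as still to be obtained.

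The willingness criterion itself can stay as it is for the cessation trial.
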